## **Introduction**

### **Background and rationale**

Asymptomatic bacteriuria (ASB) is a condition in which bacteria from the bowel are detected in significant numbers by culture of a specimen of collected urine, but the patient does not have genitourinary symptoms or signs.(1) In contrast, urinary tract infection (UTI) is the presence of bacteria in urine specimens with defined symptoms or signs.(2, 3) Catheter-associated urinary tract infection (CA-UTI) is defined as presence of bacteria in urine specimens with defined symptoms or signs in the presence of an indwelling urinary catheter, and catheter-associated asymptomatic bacteriuria (CA-ASB) is defined as presence of bacteria in urine specimens without defined symptoms or signs in the presence of an indwelling urinary catheter.(2) The use of inappropriate antibiotic treatment for ASB is a systemic antibiotic

stewardship problem, causing harm due to antibiotic adverse effects, selection of bacteria toward drug resistance, and wasted cost.(4)

UTI's are among the commonest indications for antimicrobial therapy. Prevalence of ASB varies from 1-5% among healthy premenopausal women, to 25-50% among women in long term care, to 100% among patients with chronic indwelling catheters.(5) Treatment of ASB with antimicrobial therapy does not reduce incidence of symptomatic UTI, complications or death, and is associated with adverse events.(6) Among women with ASB randomized to treatment, resistance to antibiotics among isolated bacteria increased.(7) Even among pregnant women, the treatment of ASB may not provide significant benefit.(8, 9) Various interventions have been proposed to reduce antibiotic treatment for ASB. Physicians have difficulty avoiding treatment when presented with positive culture results.

Recognizing the inappropriate treatment of ASB to be a problem in acute care, a novel intervention was defined, in which identification and susceptibility results for positive urine culture results were not made available to physicians, unless the physician called the microbiology laboratory.(10) This “modified reporting” was associated with a reduction in the rate of antibiotic treatment of AB from 48% to 12% (number needed to report for benefit = 3) among non-catheterized inpatients, using historical controls.

A randomized, unblinded controlled trial was performed in St. John's, among patients without indwelling catheters, using the same intervention.(11) Results of positive urine cultures from 110 consecutive inpatients at two urban acute care hospitals were randomised to standard report or modified report. Specimens randomized to the modified report were reported as follows: “This POSITIVE urine culture may represent asymptomatic bacteriuria or urinary tract

infection. If urinary tract infection is suspected clinically, please call the microbiology laboratory for identification and susceptibility results.”

Exclusion criteria were age less than 18 years, pregnancy, presence of an indwelling urinary catheter, samples from patients already on antibiotics, neutropenia, or admission to an Intensive Care Unit. Patients were followed for seven days, and physician treatment decisions were observed. 76/110 (69%) of positive urine cultures represented ASB. The proportion of appropriate treatment (UTI treated plus ASB not treated) was higher in the modified arm than in the standard arm (44/55 (80.0%) vs 29/55 (52.7%), absolute difference=-27.3%, RR=0.42, p=0.002, Number needed to report for benefit=3.7).

There were two bacteremias in the modified report group, and one bacteremia in the standard report group, none of which were considered related to the intervention. There were two deaths in the modified report group, and one death in the standard report group, none of which were considered related to the intervention. Based on this trial, the intervention was considered safe over 7 days of followup, and effective to reduce inappropriate treatment, but further study would be required among populations excluded from the trial.

We propose to repeat the trial using an identical design and intervention, but including only urine collected from indwelling catheters. The control arm is standard of care. We hypothesize that the modified reporting intervention will also demonstrate effectiveness at reducing treatment of ASB in this population, without causing harm.

## **Objectives**

Research Question: Among inpatients with positive urine cultures collected from indwelling catheters reported by Health Sciences microbiology laboratory, would restricted

reporting, as compared to standard reporting, lead to a reduction in the rate of inappropriate antibiotic therapy without an increase in bacteremia or death?

### **Trial design**

Randomized controlled trial, 2 parallel groups with equal allocation, superiority analysis.

### **Methods: Participants, interventions, and outcomes**

The proposed study is a randomized trial of two methods of laboratory reporting in which physicians are the main research participants. At the time of positive urine culture results, the specimen will be randomized by computer generated random number placed into serially numbered sealed, opaque envelopes, into two equal groups. One group will receive modified reporting, and the other group will receive standard reporting of identification and susceptibility. Physicians will then have the option of calling the laboratory to receive the results or not. Complete results will be released by telephone and laboratory information system to physicians who call to request them. Physicians will be informed about the study prior to initiation, and debriefed about the study after the results have been collected.

The definition of CA-UTI will be based on the Infectious Diseases Society of America guidelines,(2) not the Centers for Disease Control National Health Safety Network surveillance definition, which is not designed for clinical care.(12) The definitions to be used in patients with indwelling urethral, indwelling suprapubic, or intermittent catheterization are as follows:

#### CA-UTI

1. presence of symptoms or signs compatible with UTI with no other identified source of infection AND
2.  $\geq 10^3$  colony-forming units (cfu)/mL of  $\geq 1$  bacterial species in a single catheter urine specimen or in a midstream voided urine specimen from a patient whose

urethral, suprapubic, or condom catheter has been removed within the previous 48 h

#### CA-ASB

1. presence of  $\geq 10^5$  cfu/mL of  $\geq 1$  bacterial species in a single catheter urine specimen in a patient without symptoms compatible with UTI.

Signs and symptoms compatible with CA-UTI include new onset or worsening of fever, rigors, altered mental status, malaise, or lethargy with no other identified cause; flank pain; costovertebral angle tenderness; acute hematuria; pelvic discomfort; and in those whose catheters have been removed, dysuria, urgent or frequent urination, or suprapubic pain or tenderness. In patients with spinal cord injury, increased spasticity, autonomic dysreflexia, or sense of unease are also compatible with CA-UTI.

The primary efficacy outcome is proportion of appropriate antibiotic therapy prescribed by physicians, based on published diagnostic criteria for ASB and UTI among catheterized patients. Appropriate therapy is defined as any treatment for UTI, or no treatment for ASB. The primary safety outcome is rate of bacteremia and death.

#### **Study setting**

Specimens will be collected from inpatients admitted to one of the two tertiary care academic hospitals in St. John's, Newfoundland, Canada. Health Sciences Center (346 acute care beds) provides medicine, pediatric and surgery inpatient services, critical care, cardiac surgery, neurosurgery, plastic surgery, burn unit, obstetrics/gynecology and acute psychiatry. St. Clare's Mercy Hospital (205 acute care beds) provides medicine and surgical inpatient services, critical care, general surgery, vascular surgery, thoracic surgery, otolaryngology, orthopedics,

and ambulatory services. The metropolitan area of St. John's has a population of 219,000 people (2017). One centralized microbiology laboratory performs all testing for the city.

### **Inclusion and exclusion criteria for participants**

Consecutive positive urine cultures collected from indwelling catheters from patients greater than or equal to 18 years of age, admitted to acute care will be included. Inpatients must be admitted to Health Sciences Center or St. Clare's Mercy hospitals only, to facilitate access to inpatient records. Exclusion criteria will include urine cultures not collected from indwelling catheters, pregnancy, antibiotic treatment at the time of collection, patients in the Intensive Care Unit and patients with blood neutrophils  $<1.0$  within 7 days, which will help protect immunocompromised individuals, and admission to a urologist.

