### **Outcomes**

Primary efficacy outcome:

Proportion of appropriate antibiotic therapy prescribed by physicians. Appropriateness is determined by investigators based on chart review, based on diagnosis of CA-UTI or CA-ASB.

Appropriateness is determined within seven days from positive urine culture.

Secondary efficacy outcomes:

Proportion of calls from physicians requesting complete report

Primary safety outcomes:

Mortality rate over seven days from positive urine culture.

Bacteremia rate over seven days from positive urine culture.

Adverse event rate over seven days from positive urine culture.

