## **Sample size**

In the previous trial of the same intervention, modified reporting increased the appropriateness of treatment from 29/55 (52.7%) to 44/55 (80.0%) ( $p=0.002$ ), for an absolute difference of +23%. Accepting a risk of type 1 error of five percent, and a risk of type 2 error of twenty percent, the study will require  $2N=90$  patients. To account for missing data, recruitment will be increased to 100 patients.

The microbiology laboratory receives 130 urine specimens per day, with 30 percent reported as significant growth (40 specimens per day). Twenty-five percent are submitted from inpatients (10 specimens per day). Approximately 33% of inpatient urines are collected from catheters, however collection method is not always provided to the laboratory. This leaves approximately three urine specimens per day which may be eligible for inclusion. In the previous trial, approximately 40% of eligible specimens were excluded based on exclusion criteria. Recruitment of 100 specimens will require approximately 60-90 days.

The statistical test to be used is a comparison of proportions between two groups (T test, two-sided analysis). Because true diagnosis may be biased by lack of access to clinical information, an intention to treat analysis including all patients randomized will be performed.

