## **Recruitment**

Every urine specimen received for culture during the study period will be assessed for inclusion.

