### **Implementation**

Allocation sequence will be generated by investigators. Investigators will enroll specimens and assign specimens to reporting interventions.

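### With no one-per-patient rule, a repeat positive culture could put one patient in both arms, which could dilute the effect and count a death or bacteremia twice

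*Combined protocol and SAP*

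**What the plan says.** The operative sections all work in specimens.

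- **Inclusion and exclusion criteria for participants:** the eligible unit is "Consecutive positive urine cultures collected from indwelling catheters".
- **Recruitment:** "Every urine specimen received for culture during the study period will be assessed for inclusion".
- **Methods: Participants, interventions, and outcomes:** "At the time of positive urine culture results, the specimen will be randomized by computer generated random number".
- **Implementation:** "Investigators will enroll specimens and assign specimens to reporting interventions".
- **Sequence generation:** simple randomisation, with no blocks or strata, so nothing links a second specimen to the patient's first allocation.
- **Statistical methods:** the intention-to-treat set is defined in specimens and compared with an unadjusted Pearson chi-squared test.

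The Sample size section switches units. It says "recruitment will be increased to 100 patients", then "Recruitment of 100 specimens will require approximately 60-90 days", and describes the intention-to-treat set in patients.

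Under Outcomes, safety is timed from the culture, for example "Mortality rate over seven days from positive urine culture". Bacteremia and adverse events use the same clock.

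The only criterion that bears on re-entry is the exclusion of patients receiving antibiotics when the specimen is collected.

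**The concern.** Patients and specimens are treated as interchangeable, but no rule makes them so. Repeats are plausible: the Background section puts the prevalence of bacteriuria at 100% with chronic indwelling catheters, so a second culture from such a patient is likely to be positive too.

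Three things are at stake.

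1. **Dilution.** A patient with one specimen in each arm may have a single treatment decision scored in both. The standard report on one specimen also shows the identification and susceptibility held back on the other.
2. **Safety counts.** A death or bacteremia inside two overlapping windows enters the table twice.
3. **Selective re-entry.** A patient still on treatment cannot re-enter; an untreated one can. The modified report is meant to reduce treatment, so re-entry may depend on the first allocation.

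**Working it through.** **Inputs from the documents.** Appropriate treatment 29/55 = 52.7% (standard) and 44/55 = 80.0% (modified); two-sided 5% test; 80% power; stated total 90, raised to 100.

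**Assumed inputs.** The number of repeat patients *k* (5, 10 or 20, two specimens each, among 100 specimens) and the share *c* of repeat patients whose two specimens share one decision (0, 0.5 or 1). Neither is in the documents.

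**Step 1: reproduce the plan's figure.**
n per arm = [1.96·√(2·p̄·(1−p̄)) + 0.842·√(p1(1−p1) + p2(1−p2))]² / (p2−p1)², with p̄ = 0.664 and p2−p1 = 0.273.
This is (1.310 + 0.538)² / 0.0744 = 45.9, so 46 per arm and 92 in total. The stated 90 is reproduced within rounding of method (the unpooled formula gives 88). It rests on the 27.3-point difference, not on the +23% printed beside it. Then 90/0.90 = 100. These calculations take every observation as a different patient.

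**Step 2: chance of entering both arms.** Under simple 1:1 randomisation with m specimens it is 1 − 2·(0.5)^m: 50% for two, 75% for three, 87.5% for four.

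**Step 3: dilution.** Half of the *k* pairs are expected to split. Suppose a split pair with carry-over shares one decision, made as under standard reporting (52.7%). Then *c·k*/2 of about 50 modified-arm specimens lose the effect, and
difference = 27.3 × (1 − *c·k*/100).

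**Step 4: power.** Power was simulated with 100 specimens, simple randomisation and a Pearson chi-squared test at 5%. In the carry-over cases, same-arm pairs with carry-over also share an outcome.

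| Repeat patients | Difference, full carry-over | Power | Difference, half carry-over | Power |
|---|---|---|---|---|
| 0 | 27.3 | 84% | 27.3 | 84% |
| 5 | 25.9 | 80% | 26.6 | 82% |
| 10 | 24.5 | 75% | 25.9 | 79% |
| 20 | 21.8 | 63% | 24.5 | 75% |

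Repeated runs agree to within about 2 points. With no carry-over the difference stays at 27.3 points and power at 83–84%. Type I error was about 5–6%.

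As a check, the closed-form power at 50 per arm is 83% for a difference of 27.3 points, 74% for 24.5 and 62% for 21.8.

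**Step 5: safety counts.** The earlier trial had 2 versus 1 deaths and 2 versus 1 bacteremias (modified versus standard). If one of the two modified-arm deaths had also belonged to a standard-arm specimen with an overlapping window, the table would read 2 versus 2. If both specimens had been in the modified arm, it would read 3 versus 1.

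**The case against.** The best counter-argument is that one culture per patient was intended. The Background section describes the earlier trial as cultures from 110 consecutive inpatients, reports 110 cultures with 55 per arm, and says the new trial repeats that design. The Sample size section also speaks of patients. That is good evidence of intent, but no operative section states the rule, and the new eligibility text refers to cultures.

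Other points limit the size of the problem, and they stand:

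- The antibiotic exclusion keeps out patients being treated at the time of the second collection. The calculation ignores this, so the full carry-over figures are an upper bound.
- Dilution needs repeats, a split allocation and carry-over. Without carry-over there is none.
- The Participant timeline and Data collection methods place the appropriateness assessment at day 2, although Outcomes allows seven days. If day 2 governs, less overlap is possible for the primary outcome.
- Physicians in the modified arm can obtain full results by telephone, so access to them is already part of that arm.
- The case of 20 repeat patients makes 40 of 100 specimens come from repeat patients, and nothing in the documents supports a figure that high.

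A reader might infer that patients will enter both arms, that the effect will certainly be diluted and safety events certainly double-counted, or that the primary test is invalid. The documents do not support these readings. They give no repeat rate, both consequences are conditional, and type I error stayed near nominal in the models above.

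**Conclusion.** The gap is real: followed as written, the plan allows a patient to be randomised more than once and into opposite arms. The consequences are possible, and their size is unknown.

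With 5 to 10 repeat patients and half carry-over, power stays at about the planned 80% (82% and 79%). A serious loss, to about 63%, needs 20 repeat patients and full carry-over. Dilution of this kind pulls the result toward no difference. The effect of selective re-entry has not been quantified.

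Double-counting depends only on overlapping seven-day windows, not on carry-over. With event counts as small as those in the earlier trial, a single instance would visibly change the safety comparison.

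**What to change.** In the Inclusion and exclusion criteria, state that only the first eligible positive catheter culture from each patient is randomised, and that later cultures from that patient are neither randomised nor restart follow-up. In Sample size and Statistical methods, use patients as the unit for the target, the intention-to-treat set and all denominators. Count each safety event once per patient.

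The protocol should also say how later, non-randomised cultures are reported, and record them, because a later report within the window can still influence the decision being scored. That choice belongs to the investigators.

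**Cost.** An eligibility sentence, consistent wording in two other sections and a check of the enrolment log. The required sample size does not change. On the Sample size section's own rates, 130 × 0.30 × 0.25 × 0.33 gives about 3.2 specimens a day (stated as about three), of which 60% remain after exclusions. One hundred specimens then take 100/(3.2 × 0.6) = 52 to 100/(3 × 0.6) = 56 days. If 20% were repeats (assumed) and were not randomised, dividing by 0.8 gives about 65–70 days, within the planned 60–90. The section warns that collection method is not always supplied, so the true time may be longer.

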### **Interventions**

The modified report states "This POSITIVE urine culture may represent asymptomatic bacteriuria or urinary tract infection. If urinary tract infection is suspected clinically, please call the microbiology laboratory at [name] between 0900 to 2300, or the microbiology technologist on-call at [name] at night, for identification and susceptibility results." The standard report provides bacterial count, bacterial identification and bacterial susceptibility results.

The report is provided to the physician approximately 24 hours after receipt of the specimen, when cultures have been examined after overnight incubation. The intervention is a single report, so it is not possible to discontinue the intervention, or change allocation during the trial. There will no other influence on concomitant care or treatment.

### **Outcomes**

Primary efficacy outcome:

Proportion of appropriate antibiotic therapy prescribed by physicians. Appropriateness is determined by investigators based on chart review, based on diagnosis of CA-UTI or CA-ASB.

Appropriateness is determined within seven days from positive urine culture.

Secondary efficacy outcomes:

Proportion of calls from physicians requesting complete report

Primary safety outcomes:

Mortality rate over seven days from positive urine culture.

Bacteremia rate over seven days from positive urine culture.

Adverse event rate over seven days from positive urine culture.

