### Participant timeline

TIMEPOINT	STUDY PERIOD			
	Enrolment	Allocation	Post-allocation	
	Day -1	Day 0	Day 2	Day 7
ENROLMENT:	Urine specimen received at microbiology laboratory	Urine culture result reported to physician	Physician treatment decision made	Safety assessment
Eligibility screen	X			
Allocation		X		
INTERVENTIONS:				
Reporting		X		
ASSESSMENTS:				
Appropriateness			X	
Adverse Events			X	X
Bacteremia			X	X
Mortality			X	X

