### **Data collection methods**

After randomization and reporting, a blinded physician investigator will assess inpatients for the true diagnosis of CA-ASB or CA-UTI at two days after reporting. Health records will be accessed including demographics, symptoms, treatment decisions and outcomes (treated CA-ASB, treated CA-UTI, untreated CA-ASB, untreated CA-UTI).

If patients are discharged from hospital before seven days, primary care physicians will be contacted by phone for additional clinical information. If patients die before seven days, available data will be analyzed.

Frequency of physician calls requesting complete reporting will be recorded.

Urine culture is reported according to laboratory protocol by licenced medical laboratory technologists, in categories of significant growth, non-significant growth, and no growth, based on quantity of growth and number of bacterial types detected. Antimicrobial susceptibility is reported according to laboratory protocol, including selected first and second-line antibiotics, as susceptible, intermediate or resistant. Drug cost and dosage suggestion are provided.

Data collection form attached.

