### **Statistical methods**

All specimens randomised and reported will be included in the Intention-to-treat (ITT) analysis. Specimens inappropriately included will be excluded from the Per-protocol (PP) analysis. The proportion of appropriate treatment will be compared using two-sided Pearson chi squared test (SPSS 23.0, IBM, USA). Adjusted analysis will not be performed. A subgroup defined as specimens in which physicians requested complete reporting will be analysed for appropriateness, compared to the standard reporting arm. Missing data will not be imputed.

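### Can the primary outcome be scored two ways, by time point (Day 2 or seven days) or by colony count?

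*Combined protocol and SAP*

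**What the plan says.** **Time of scoring.** The Outcomes section gives an outer limit: "Appropriateness is determined within seven days from positive urine culture". The Participant timeline has one mark for appropriateness, in the Day 2 column headed "Physician treatment decision made". Its Day 7 column is headed as a safety assessment and carries marks only for adverse events, bacteremia and mortality. Data collection methods says that "a blinded physician investigator will assess inpatients for the true diagnosis of CA-ASB or CA-UTI at two days after reporting". The same section has primary care physicians telephoned when a patient leaves hospital before seven days, without saying whether that information can alter the score. Background and rationale describes the prior trial, whose design is to be repeated: "Patients were followed for seven days, and physician treatment decisions were observed".

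**Classes.** CA-UTI needs compatible symptoms or signs plus at least 10^3 cfu/mL. CA-ASB needs at least 10^5 cfu/mL of one or more "bacterial species in a single catheter urine specimen in a patient without symptoms compatible with UTI". Appropriateness is defined for these two diagnoses only, and Data collection methods lists four outcome cells: each diagnosis, treated or untreated. Eligibility is any positive catheter culture. The laboratory reports growth "in categories of significant growth, non-significant growth, and no growth, based on quantity of growth and number of bacterial types detected", with no numerical cut-off given.

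**Analysis set.** Under Statistical methods, "All specimens randomised and reported will be included in the Intention-to-treat (ITT) analysis", and missing data are not imputed.

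**The concern.** The outcome definition names a window and the schedule names a day. No sentence says which treatment status counts if it changes between them, or whether signs first documented after the report count towards the diagnosis. A patient first treated on Day 4 is untreated on one reading and treated on the other. For CA-UTI that turns inappropriate into appropriate; for CA-ASB it does the reverse.

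An asymptomatic specimen at 10^3 to below 10^5 cfu/mL meets neither definition and so has no score, yet the intention-to-treat set is meant to hold every specimen randomised and reported.

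If both gaps were live, the same charts could yield two primary results. The analyst is unblinded (Blinding) and the trial stops if the interim is significant (Data monitoring), so a scoring choice made after seeing data would be a real weakness.

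**Working it through.** **1. The time point, section by section.**

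| Section | What it fixes |
|---|---|
| Outcomes | Outer limit of seven days |
| Participant timeline | Appropriateness at Day 2 only; Day 7 is safety |
| Data collection methods | Diagnosis at two days after reporting |
| Background and rationale (prior trial) | Seven days of follow-up, decisions observed |

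Day 2 satisfies all four rows. A seven-day score would need a Day 7 review of diagnosis and treatment, and the schedule has none. The prior-trial sentence reports length of follow-up, not the day on which treatment was scored. An investigator following the schedule scores at Day 2.

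**2. The count gap.** It is non-empty only if the laboratory calls an asymptomatic specimen below 10^5 cfu/mL positive. The Sample size section draws its recruitment estimate from cultures reported as significant growth, a category set by a laboratory protocol that is not in the documents. If such a specimen were enrolled, the assessor would have four cells. Without compatible symptoms both CA-UTI cells are closed, which leaves CA-ASB.

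**3. The plan's own sample size.** Inputs: p1 = 29/55 = 0.527, p2 = 44/55 = 0.800, two-sided alpha 0.05, power 0.80 (Sample size); equal allocation (Trial design). Pooled formula, with p̄ = 73/110 = 0.664:

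n = [1.960·√(2p̄(1−p̄)) + 0.842·√(p1(1−p1) + p2(1−p2))]² / (p2−p1)² = (1.310 + 0.538)² / 0.0744 = 45.9, so 46 per arm, total 92 against the stated 90 (the unpooled formula gives 88).

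**4. Sensitivity to single scores.** Uncorrected Pearson test with m per arm: χ² = d² / [p̄(1−p̄)·2/m]. Check on the prior trial, 29/55 vs 44/55: p = 0.0025 (stated 0.002). The rows below use arms of 25 and 50 at about the prior rates.

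| Table | d | p̄ | χ² | p |
|---|---|---|---|---|
| 13/25 vs 20/25 | 0.28 | 0.66 | 4.37 | 0.037 |
| 13/25 vs 19/25 | 0.24 | 0.64 | 3.13 | 0.077 |
| 13/25 vs 21/25 | 0.32 | 0.68 | 5.88 | 0.015 |
| 26/50 vs 40/50 | 0.28 | 0.66 | 8.73 | 0.003 |
| 26/50 vs 36/50 | 0.20 | 0.62 | 4.24 | 0.039 |
| 26/50 vs 35/50 | 0.18 | 0.61 | 3.40 | 0.065 |

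One specimen is 1/25 = 4 points at the interim and 1/50 = 2 points at the end. These are net changes; flips in opposite directions cancel.

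**5. Unscorable specimens.** Assume a share u is dropped from 50 per arm. Power = Φ{[(p2−p1)√n − 1.310] / √(p1(1−p1) + p2(1−p2))}, where the denominator is 0.640.

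| u | n per arm | Power |
|---|---|---|
| 0% | 50 | 83.3% |
| 5% | 47.5 | 81.4% |
| 10% | 45 | 79.2% |
| 15% | 42.5 | 76.8% |

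The increase from 90 to 100 already covers a 10% loss.

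**The case for a change.** The strongest opposing case is that an outcome definition should stand alone, and this one states a window rather than a day. The ambiguity may also differ between arms. Physicians in the modified arm must telephone for full results, so treatment could start later there, and a Day 2 score would then count some eventually treated CA-UTI as inappropriate. That is a plausible inference, but the documents give no frequency for it. It also describes a consequence of scoring at Day 2, not a doubt about whether the plan does so.

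The size could be larger than the dropout figures suggest. If an assumed 5% or 10% of scores flipped at random between Day 2 and Day 7, the difference would shrink from 27.3 to 24.5 or 21.8 points, and power with 50 per arm to 73.6% or 62.1%. If 10% of specimens were unclassifiable but kept, scoring all of them inappropriate gives 47.5% vs 72.0%, and scoring all of them appropriate gives 57.5% vs 82.0%. These figures stand as arithmetic. The first set treats one window as a noisy copy of the other, which does not arise when the schedule's single window is used. In the second, the difference is the same either way (0.9 × 27.3 = 24.5 points); the convention moves the level of both arms.

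The unblinded analyst, the stopping rule, and the absence of a monitoring committee and of auditing are fairly cited. Against them, a blinded assessor makes the diagnosis, and a second investigator reviews the data before the dataset is locked (Blinding; Data management). The attached data collection form is not in the documents and may carry the scoring instructions.

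What remains is that no sentence says a treatment change after Day 2 is disregarded, and the laboratory cut-off is unstated.

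**Conclusion.** The concern does not call for a change. On timing, the Outcomes wording is looser than the schedule but compatible with it, and the two sections that direct the work both point to Day 2. On counts, the gap between the definitions is logically real, but whether any enrolled specimen falls into it is unknown, and the four-cell recording has a natural answer if one does. Following the plan as written gives a sound primary result; both points are details that investigators would settle sensibly.

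The size is modest on the assumptions shown: five net changes in the modified arm to lose significance at the final analysis at the prior trial's rates, and 79.2% power if 10% of specimens were dropped. The interim's dependence on one specimen reflects a table of about 25 per arm close to 0.05, and it runs both ways (p = 0.077 or p = 0.015). Nor would a matched seven-day sensitivity analysis be free, since no Day 7 review of diagnosis and treatment is scheduled.

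This rests on reading the schedule as governing and on the frequency of affected specimens being small, which the documents neither confirm nor contradict.
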